10.8 Sampling

10.8.1 Safety Sample Collection (Clinical Chemistry, Hepatic function and Haematology)

Please see schedule above and the INCA laboratory manual.

10.8.2 Research Sample Collection

Samples for future research will only be collected from participants who provide written informed consent at screening and if registered onto trial a further sample will be collected at 120 day.

A 30ml blood sample (research) will be collected at screening and day 120 in 3 x 10ml Vacutainer Serum Separating tubes (SST). These samples will be collected at the same time as samples taken for monitoring safety bloods. However, if a participant decides to withdraw from study before day 120 and is willing, the day 120 blood sample may be collected at an earlier visit if consented.

Sample kits will be provided by the LCTC.

10.8.2.1 Sample Processing, Storage and Handling

Samples are to be processed on site as serum and stored at -20°C before being transferred to the Rheumatology labs in the Clinical Sciences Centre Aintree, Liverpool (3rd floor Clinical Sciences Centre). A log of time between sampling and freezing will be recorded.

Serum samples from the St Thomas' site will be transferred to Clinical Sciences Centre Aintree, Liverpool at the end of the study and where needed also during the study. Transfer of samples will be co-ordinated by the LCTC who will arrange a courier.

Once transferred to Liverpool, samples will be stored at -80°C at the University of Liverpool labs based in the Clinical Sciences Centre, Aintree University Hospital.

Custodianship

Research samples will be stored for up to 25 years for future analysis of immune mediators or antibodies relevant to CPRS. The custodian of the samples is [name].

10.9 Intervention Discontinuation and Participant Discontinuation/Withdrawal

In consenting to the trial, participants agree to all trial activities including administration of trial intervention and treatment and follow-up assessments/visits and data collection. Every effort should be made to facilitate the completion of these for every recruited participant. If it is not possible to complete these activities (or it is deemed inappropriate) the reasons why should be documented. The following sub-sections describe the different levels of discontinuation/withdrawal.

Premature Discontinuation of Trial Intervention

Participants may discontinue treatment for reasons including, but not limited to:

- Patient-led i.e. request by the patient / legal representative / consultee
- Unacceptable toxicity (see Section 13 for AE reporting)
- Intercurrent illness preventing further treatment.
- CRPS symptom progression which requires discontinuation of therapy or results in inability to continue to comply with study procedures
- Pregnancy
- Death
- Clinician-led:
 - Any change in the participant's condition that justifies the discontinuation of treatment in the clinician's opinion.
 - Reasons of non-adherence or non-compliance with treatment or other trial procedures
 - Participant meets an exclusion criterion (either newly developed or not previously recognised)
 - Participant unable to receive Anakinra for >=7 days consecutively

Discontinuation from Anakinra does not mean discontinuation of the study altogether, and the remaining study procedures, follow up assessment/visits and data collection should be completed as indicated in the protocol unless the patient requests to withdraw from further follow up visits. Data to be collected at the time of discontinuation will include the following:

- 1. Reason for discontinuation (if available)
- 2. Any AEs
- 3. Pain intensity score (NRS)

If a study participant is discontinued from the study early, an End of treatment CRF will be completed describing the reason for discontinuation. In situations where treatment is withdrawn due to an AE, participants will be followed up until resolution of that AE or determination that the participant's condition is stable. All AEs will be followed up until 180 day.

In case of a Participant Withdrawal the participant will be assessed for AEs, if any, and medication use.

Participant Withdrawal from Follow Up

Participants are free to withdraw from follow up at any time without providing a reason, though a reason should be recorded if one is given. Those who wish to withdraw from further follow-up will have the data collected up to the point of that withdrawal included in the analyses. The participant will not contribute further data to the study unless this is required by law (e.g. safety events).

The LCTC should be notified of withdrawals from the study as soon as possible, a completed Withdrawal from Study CRF must be returned to the LCTC within 7 days.

In situations where study withdrawal is due to an AE, participants will be followed up until resolution of that AE or determination that the participant's condition is stable.

In case of premature discontinuation, the participant will be assessed for AEs, if any, and medication use.

Participant Transfer

If a patient moves from the area, every effort should be made for the patient to continue in the trial if they are happy to travel to site from their new location. If they are no longer able to continue with study visits (and therefore study treatment) every effort should be made by the site to follow up the patient as far as is possible. The trial provides financial support to participants of travel expenses of up to £20 per visit.

Loss to Follow-up

A participant will be considered lost to follow up if s/he fails to return for 2 scheduled visits and is not contactable by the site research team.

If a participant fails to attend/facilitate a required study visit the following actions must be taken:

- Site will attempt to contact the participant and reschedule the missed visit and advise the participant on the importance of maintaining the assigned visit schedule.
- Before a participant is deemed to be lost to follow up, site research staff will make every effort to regain contact with the participant (i.e. 3 telephone calls and, if necessary, a headed letter to last known address). These efforts should be recorded in the participants medical notes.
- If the participant continues to be unreachable they should be considered withdrawn from the study with a primary reason of lost to follow up and this should be recorded on the appropriate CRF.

10.10 End of Trial

This will be defined as the date on which data for all participants are frozen and data entry privileges are withdrawn from the trial database. The trial may be closed prematurely by the TSC, on the recommendation of the IDSMC.

Site and closure activities will be centrally coordinated and conducted in accordance with LCTC processes regardless of whether the trial closes as planned or prematurely. This includes activities such as:

- End of Trial notification to REC and competent authority e.g. MHRA.
- Trial-related materials reconciled and returned/disposed of as appropriate see section 8.
- All site data entered onto the study database, discrepancies raised and satisfactory responses received.
- Quality Control (QC) checks of the ISF, PSF and TMF as appropriate.

Study Discontinuation

The CI reserves the right to suspend or terminate the study, but intends to only exercise this right for valid scientific reasons or reasons related to the protection of subjects. The trial may be closed prematurely by the TSC based on recommendations of the IDSMC.

Possible reasons for study termination include:

- Insufficient registration to complete the study within the expected timeframe as per progression rules in section 11.
- Identification of unacceptable safety profile; suspicion of an unacceptable risk will result in a suspension, confirmation of an unacceptable risk will result in termination. See section 13.
- Product performance/product supply issues.
- Discontinuation of product.

In cases of study suspension/termination, medical care will continue to be provided to participants registered in the study (e.g. assessment for AEs, programming parameter changes to address safety concerns/participant discomfort). Participants will be notified by the investigator of suspension/termination due to unacceptable risk or of termination due to any other cause.

11 PROGRESSION CRITERIA

Monitoring for clinical trial progress will focus on recruitment and safety. This will be done by the IDSMC.

The following factors will be used to inform the decision to progress into the next stage of the trial:

- 1. **Recruitment**. Assessed 6 months from recruitment start. Initial recruitment rate of 0.5 participants each month per centre for the first 6 months from recruitment start.
- 2. **Safety**. Assessed 12 months from recruitment start (or later if it takes longer for 10 participants to be registered): For the first 10 registered participants, 3 or less reporting persistent pain (greater than 1 week) at injection site of at least moderate intensity (5 or greater on a 0-10 NRS scale) or substantial CRPS pain increase (>=2points NRS), ongoing for >1 month despite and from the time of pain-related treatment stop.
- 3. **Safety**. Assessed 12 months from recruitment start: Consider stopping if 30% or greater of study participants experiencing a serious adverse reaction (SAR).
- 4. **Recruitment and adherence**: At 12 months from recruitment start to have at least 12 participants registered and at least 50% of registered participants completing their active treatment.
- 5. **Futility**. After 12 participants have been recruited and completed 4 months treatment period, an average of no pain increase among completed participants (to visit 5/ 120 day) and at least one participant reporting at least 2 points of pain reduction on the NRS (rounded to the nearest whole number), both these criteria referring to the average pain recordings over the last two weeks before visit 5 / 120 day compared to baseline (0 day).

The IDSMC will use the above progression rules as a guide during regular monitoring with regards to trial progress and will provide a recommendation to the TSC concerning continuing the study. The above are not intended as strict stop/start criteria.

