^{**} Additional pregnancy tests may be conducted during the participation of the trial if there is any suspicion of being pregnant

^{***} Type of Clinical assessment will be only completed if at a visit. If completed by phone no clinical assessment will take place

[~] May be taken at earlier timepoint if participant withdraws before day 120.

⁺ unblinded QST

[#] Study Completion

All follow up visits will be scheduled from baseline (Day 0). Each participant will complete treatment administration from day 0 to day 120 and will be followed up for 180 days in total. During this time, scheduled follow ups will be conducted via both telephone as well as clinic visits. No face to face study visits are planned after 120 days.

Following registration each participant will be given a diary that they will fill in and record their pain intensity in accordance with the schedule:

- Weekly between day 0 to day 90
- Daily Between day 90 to day 120
- Weekly between day 120 to day 180

Clinic Follow-Up Visits:

Participants will need to attend clinics for follow-up at 30, 60, 90 and 120 days. These visits should be arranged at the baseline visit post registration. The following data should be collected and assessments/activities performed at all visits (unless specified differently below):

- Concomitant medication
- AEs
- Further Provision of Anakinra
- Collection of safety blood samples
- Collection of research blood samples (30ml, day 120 only)
- · Clinical assessment and examinations including:
 - o Pain assessment on NRS from their pain diaries
 - o Limb Volume (days 60 and 120 only)
 - o Vital signs: BP, HR, and weight

Telephone follow ups:

Research nurses (RNs) will telephone participants approximately 2 weeks (+/-3 days) after each clinic visit up to day 120 when the last drug dose is administered, and a final telephone follow up at day 180 at the end of the trial. Telephone appointments will be arranged and conducted by local research teams. The following information should be collected and recorded on the appropriate CRF:

- Concomitant medication
- AEs
- Pain assessment up to 120 days at the end of drug administration (NRS)
- EQ5D-5L questionnaire at day 180

Efficacy Assessments

This trial is not designed to determine efficacy, however data will be collected on outcomes that will be used to determine efficacy in a future definitive trial. Outcomes are detailed in section 9.

Safety Assessments

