25.1.2.2 Safety

The frequency and proportion of participants, denominator used as the number registered, who have experienced the below will be summarised:

persistent pain (greater than one week) at the injection site of at least moderate intensity (≥

5 on a 0-10 NRS scale)

• a substantial CRPS pain increase of  $\geq$  2 points NRS, ongoing for more than 1 month despite

and from the time of pain related treatment stop.

SARs

The substantial pain increase will be calculated as: CRPS pain at day X – CRPS pain at day (X-30), where X is >30. Persistent pain will be derived from the pain dairies and adverse events. Both substantial pain increase and persistent pain are collected throughout the trial as Adverse events and are particularily asked about at each visit (see forms 5 – Telephone Follow up, 6 Follow up and 7 Final Telephone follow up). The yes/no response at each visit and the derived substantial pain increase/persistent pain will

both be used to ensure all events are captured.

If 3 or less patients report persistent pain or substantial pain increase across the first 10 participants

registered this criteria will have been met.

However, stopping will be considered if 30% or more of study participants experience an SAR in the first 12 months of recruitment.

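### Safety progression criterion 2 is timed by registration of the tenth participant with no follow-up condition, so late registrations bias it towards being met

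*Protocol*

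**What the plan says.** Protocol section 11, item 2 sets the timing: "Assessed 12 months from recruitment start (or later if it takes longer for 10 participants to be registered". The threshold is "For the first 10 registered participants, 3 or less reporting persistent pain (greater than 1 week) at injection site" of at least moderate intensity, or a substantial CRPS pain increase (2 or more NRS points) that is "ongoing for >1 month despite and from the time of pain-related treatment stop". The footnotes to SAP 18.1.2 give the same timing.

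SAP 25.1.2.2 applies the rule: "If 3 or less patients report persistent pain or substantial pain increase across the first 10 participants" registered, the criterion is met. Its summary line reads "The frequency and proportion of participants, denominator used as the number registered". The derivation ("The substantial pain increase will be calculated as: CRPS pain at day X" minus the value 30 days earlier) is limited to X above 30. The SAP also uses the yes/no answers on the visit forms, but these do not shorten the required duration.

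On exposure, Protocol 10.7 states: "Each participant will complete treatment administration from day 0 to day 120 and will be followed up for 180 days in total". Item 5 of section 11 (futility), by contrast, waits until 12 participants have finished the 4-month treatment period. Section 11 closes by calling the rules a guide for the IDSMC rather than strict criteria.

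**The concern.** The rule counts events among ten people but is timed by when the tenth enters, not by how long the ten have been observed. On the natural reading, when the clause for slow registration applies, the check falls at the tenth registration. That participant then has about 0 days of follow-up and cannot have met either limb of the definition, since even injection-site pain must last more than 1 week. The participants registered just before may also be too early for the CRPS-pain limb. All of them stay in the ten as event-free. The error runs in one direction only, towards declaring the condition-specific safety check met.

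**Working it through.** **Inputs from the documents.** Ten participants, met if 3 or fewer have an event (Protocol 11, SAP 25.1.2.2). Treatment to day 120, follow-up to day 180 (Protocol 10.7). Accrual of 1 per month over both sites for 6 months, then 2 per month for 12 months (Protocol 14.2.1). Most adverse events are seen at 4 weeks (Protocol 5.2.1).

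**Assumed, not in the documents.** True event probability p of 0.3 to 0.5, evenly spaced registrations unless stated, and the three event timings in step 4. One month is taken as 30.44 days.

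**1. Planned accrual.** 6 × 1 + 12 × 2 = 30, which matches the planned sample size if the second 12 months are months 7–18. The tenth registration falls at month 6 + 4/2 = 8. At month 12 the shortest follow-up is 4 months, or 122 days.

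**2. Event window.** A CRPS-pain event tied to a stop on day s is confirmable at about day s + 31. That is day 31 at the earliest and 120 + 31 = day 151 for a stop at day 120. Injection-site pain is confirmable from about day 8.

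**3. Follow-up of the first ten at assessment.**

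| Accrual | Shortest follow-up (days) | Under 31 | Under 120 | Under 151 |
|---|---|---|---|---|
| As planned, month 12 | 122, 137, 152 | 0 | 0 | 2 |
| Even, first at month 0, tenth at month 12 | 0, 41, 81, 122 | 1 | 3 | 4 |
| Even, first at month 0, tenth at month 18 | 0, 61, 122 | 1 | 2 | 3 |
| Six by month 6, last four in month 13 | 0, 8, 15, 23 | 4 | 4 | 4 |

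**4. Chance of meeting the criterion.** The documents state no such figure. With full follow-up it is P(X ≤ 3) for X ~ Binomial(10, p): 0.650 at p = 0.3, 0.382 at 0.4 and 0.172 at 0.5. With truncated follow-up, participant i has a visible event with probability p × F(t_i), and the count is Poisson-binomial. The timings are:

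- (a) Onset uniform over 4 months and countable 1 month later: F(t) = (t − 1)/4 for t between 1 and 5 months, 0 before and 1 after.
- (b) CRPS pain with onset and stop at day 28: countable at day 28 + 31 = 59.
- (c) Injection-site pain with onset at day 28: countable at day 28 + 7 = 35.

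Tenth at month 12, timing (a): the F values are 0, 0.083, 0.417, 0.75 and six of 1, which sum to 7.25. At p = 0.5, 3.6 of 5.0 expected events are visible. Under (b) two participants are below 59 days, so the count is Binomial(8, p). Under (c) one is below 35 days, giving Binomial(9, p).

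Tenth at month 18, timing (a): 0, 0.25, 0.75 and seven of 1 sum to 8.0, so 4.0 of 5.0 are visible. Under (b) and (c) one participant is too early, giving Binomial(9, p).

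| P(criterion met) | p = 0.3 | p = 0.5 |
|---|---|---|
| Full follow-up | 0.65 | 0.17 |
| Planned accrual, (a) | 0.68 | 0.20 |
| Planned accrual, (b) or (c) | 0.65 | 0.17 |
| Month 12, (a) | 0.86 | 0.47 |
| Month 12, (b) | 0.81 | 0.36 |
| Month 12, (c) | 0.73 | 0.25 |
| Month 18, (a) | 0.80 | 0.37 |
| Month 18, (b) or (c) | 0.73 | 0.25 |

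**5. Sensitivity.** If the ten are spaced 1.2 months apart (first at month 1.2, tenth at month 12), timing (a) gives 0.87 and 0.50, so the upper ends above are not strict maxima. In the bunched row of step 3, all four late registrants are invisible to the CRPS-pain limb. The count is then Binomial(6, p): at p = 0.4 the criterion is met with probability 0.82 against 0.38.

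**The case against.** Several points on the other side stand.

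- The clause ("or later if it takes longer for 10 participants to be registered") sets an earliest time, not a date. Assessment at the tenth registration is the natural reading but not the only one.
- Section 11 makes the rules a guide. The IDSMC reviews safety at least annually (Protocol 14.3, SAP 18.1.1) and receives numbers still in follow-up and compliance by 30-day period (SAP 25.1.1). Suspicion of an unacceptable risk leads to suspension whatever criterion 2 says (Protocol 10.10).
- With only ten evenly registered by month 12, criterion 4 (12 registered) is missed. So is criterion 1: five have registered by month 6, against 0.5 × 2 × 6 = 6. Criterion 2 would not carry the decision to continue alone.

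Three stronger readings are tempting but unsupported. First, a reader might infer that the check is passed by a cohort not yet at risk. Self-injection starts on the day of registration (Protocol 10.6), and under even slow accrual at least six of the ten have their full window. The fault is incomplete follow-up in the last few. Second, a reader might infer that the rule fails precisely where the slow-registration clause applies. The month-12 case does not need that clause, and under even accrual the bias is smaller at month 18 than at month 12. Third, a reader might infer that recent registrants cannot have any event. The injection-site limb needs only just over 1 week, so the long delay belongs to the CRPS-pain limb.

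None of this supplies the missing follow-up condition. The SAP would still report the criterion as met, and that report goes to the IDSMC.

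**Conclusion.** The concern holds as an omitted follow-up condition that makes criterion 2 easier to meet when the tenth registration comes close to or after month 12. With even accrual one of the ten has under 31 days, and two to four have under 120–151 days; bunched late accrual is worse. At planned accrual the effect is negligible. With the tenth at month 12, the chance of meeting the criterion is about 25–47% instead of 17% at a 50% event rate, and 73–86% instead of 65% at a 30% rate. At month 18 it is about 25–37% and 73–80%. The direction follows from the text; the sizes rest on the assumed event rates, onset timing and spacing. Because the rule is non-binding and safety review continues alongside it, the consequence is moderate: the written rule should be changed, but participants are not left without oversight.

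**What to change.** In Protocol 11 item 2, SAP 18.1.2 and SAP 25.1.2.2:

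- Keep the month-12 look, as a running count of events among those registered so far, listing each participant's days of follow-up.
- Make the formal read of criterion 2 when each of the first ten has completed the definition's own window: end of treatment or earlier stop, plus more than 1 month. A trigger at day 120 would be too early, because a stop at day 120 is not confirmable until about day 151.
- State how a participant lost before completing the window is counted.

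This follows item 5, which already ties futility to completed treatment. It needs wording only: day 151 lies within the scheduled 180 days, so no new data are collected. The cost is that under slow accrual the formal read comes about 5 months later (151/30.44 = 5.0). The month-12 running count and the continuing IDSMC safety review offset that delay.

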13.12 Investigator Reporting Responsibilities

The PI is responsible for ensuring that all safety events requiring recording on this study (see section 13) which the local research team becomes aware of are reported to LCTC. It is the responsibility of an appropriately medically qualified person as recorded on the Delegation Log to assess the seriousness and causality of events. When documenting any AEs, the correct medical terminology **must** be used.

All safety events must be recorded on an AE form and a copy of the form transferred to LCTC within seven days of the site team becoming aware of the event.

Safety events which meet the definition of "serious" must be reported in more detail to the LCTC on an SAE form and reported **immediately and in no circumstances later than 24 hours from becoming aware** unless the SAE is specified in the protocol as not requiring immediate reporting (see Section 13).

The SAE form should be completed by an appropriately delegated member of the research team; the assessments of seriousness and causality must be performed by an appropriately medically qualified person. Minimum reporting information must be provided in initial reports for all studies.

N.B. In the absence of a delegated medically qualified person the form should be completed and signed by an alternative member of the research site trial team and submitted to the LCTC. As soon as possible thereafter the responsible investigator should check the SAE form, make amendments as appropriate in line with GCP, sign and re-send to the LCTC. The initial report shall be followed by detailed follow-up reports as appropriate.

Safety events should be reported to the site R&D team in accordance with local policy.

Separate guidance are provided regarding appropriate completion of serious safety events.

REPORTING AN INITIAL OR FOLLOW-UP SAE

The investigator should ensure the actions below are completed for all reportable SAEs:

- 1) Research sites should telephone the appropriate trial team on [contact]** to advise that an SAE report will be submitted as soon as possible.
- 2) The SAE form should be emailed securely to [contact] within 24 hours of becoming aware of the event. If email is not available please contact the trial team on [name].
- 3) The responsible investigator must notify their R&D department of the event (as per standard local governance procedures).

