14.2.1 Feasibility of Sample Size

Between the two recruiting sites we expect a recruitment rate of one patient every month (across the two centres) for the first 6 months from commencing recruitment. In the second 12 months recruitment rate will be expected to be two patients monthly across both sites.

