14.3 Interim Analyses

The trial will be assessed at regular intervals (at least annually) by the IDSMC. The IDSMC will be asked to review the conduct of the trial in terms of patient recruitment and safety/toxicity. Assessments of the primary endpoint shall be presented to the IDSMC in terms of the proportion of participants tolerating Anakinra and the safety of Anakinra in participants with refractory moderate to severe CRPS. The IDSMC will be asked to make a recommendation as to whether the study assessments presented at each meeting justify continuation of further patient recruitment and/or remaining follow-ups in accordance with the study protocol and guidelines on progression (as detailed in section 11 of the protocol).

•

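### No document requires the IDSMC to check the first-10 safety limit before month 12, although the limit can be irreversibly exceeded months earlier

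*Protocol*

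**What the plan says.** Protocol section 11, item 2, sets the limit: "For the first 10 registered participants, 3 or less reporting persistent pain (greater than 1 week) at injection site", or a CRPS pain rise of at least 2 NRS points that is "ongoing for >1 month despite and from the time of pain-related treatment stop". The check is "Assessed 12 months from recruitment start (or later if it takes longer for 10 participants to be registered"). SAP 18.1.2 repeats this timing, including "or later if it takes longer for 10 participants to be registered". SAP 25.1.2.2 gives the pass rule: "If 3 or less patients report persistent pain or substantial pain increase across the first 10 participants".

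On oversight, Protocol 14.3 states: "The trial will be assessed at regular intervals (at least annually) by the IDSMC". Section 4.8 lets the IDSMC set its own meeting frequency, with the same annual floor. The only progression item dated earlier is item 1, at month 6, which concerns recruitment. Section 11 describes the rules as guidance for the IDSMC and not as strict stop/start criteria.

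On data flow, Protocol 13.12 requires an AE form for every safety event, with "a copy of the form transferred to LCTC within seven days of the site team becoming aware of the event". SAP 25.1.2.2 notes that both pain events are asked about specifically at each visit.

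On accrual, Protocol 14.2.1 states: "we expect a recruitment rate of one patient every month (across the two centres) for the first 6 months from commencing recruitment". It then expects two per month across both sites in what it calls the second 12 months. Under Protocol 10.6, participants begin anakinra on the day they are registered.

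**The concern.** The criterion is a count of participants with an event among a fixed set of 10. Such a count can only rise, so a 4th qualifying participant settles the criterion whatever happens to the rest of the 10. The date attached to it can move later but never earlier. Between the 4th event and month 12, recruitment and dosing may therefore continue with no required IDSMC look at a limit already passed, and the wait adds nothing to the pass/fail answer on this item.

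This matters because item 2 is the only numeric progression limit for the two condition-specific harms in the primary outcome. These events need not be serious, so the 24-hour SAE route would not necessarily bring them forward. The serious-reaction threshold in item 3 counts different events and is also dated month 12. Protocol 5.2 says that anakinra has not been studied in CRPS, and 5.3.1 singles out injection-site pain as a risk to be monitored carefully.

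**Working it through.** **Inputs from the documents.** N = 30 (Protocol 14.2); accrual of 1 per month to month 6, then 2 per month (14.2.1); limit of 3 of the first 10 and check at month 12 or later (section 11, item 2); at least 12 registered at month 12 (item 4); drug started on the day of registration (10.6). The documents give no expected event rate and no distribution of time to a qualifying event.

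**Step 1: reproduce the plan's own figure.** Read the second 12 months as months 7-18. Then N(t) = t for t ≤ 6, and N(t) = 6 + 2(t − 6) up to month 18. N(18) = 6 + 24 = 30, the planned sample size. If the phrase instead means months 13-24, with 1 per month assumed for months 7-12, N(12) = 12 and 30 is reached at month 21. Months 7-18 is the reading that returns exactly 30 at the end of the stated period.

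**Step 2: starts between the 10th registration and month 12.**
- Planned accrual: N(8) = 10 and N(12) = 6 + 12 = 18, so 18 − 10 = 8.
- One per month throughout, which just meets item 4: the 10th is registered at month 10 and N(12) = 12, so 12 − 10 = 2.
- An intermediate case: the current duration of 26 months and 2 weeks, less 180 days of follow-up, leaves about 20.5 months for recruitment. With 6 in the first 6 months and an even rate after (assumed), the rate is 24/14.5 = 1.66 per month. Then N(12) = 6 + 6 × 1.66 = 15.9, or 15 whole participants, and 5 start after the 10th.

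**Step 3: starts after a breach at month t, N(12) − N(t).**

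| Breach at month | Planned accrual | 1 per month |
|---|---|---|
| 4.25 (earliest: first four all qualify, just over 1 week after the 4th registers) | 13.75 | 7.75 |
| 6 | 12 | 6 |
| 7 | 10 | 5 |
| 8 | 8 | 4 |
| 9 | 6 | 3 |
| 10 | 4 | 2 |

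**Step 4: how likely a breach is.** P(X ≥ 4) = 1 − Σ C(10,k) p^k (1 − p)^(10 − k), k = 0 to 3. At p = 0.30 this is 1 − (0.028 + 0.121 + 0.233 + 0.267) = 0.35.

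| True rate | 10% | 20% | 30% | 40% | 50% |
|---|---|---|---|---|---|
| P(4 or more of 10) | 0.01 | 0.12 | 0.35 | 0.62 | 0.83 |

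**Step 5: further starts given a breach.** Simulation with 10,000 runs per setting. Each of the first 10 has an event with probability p, and time from registration to qualifying is uniform over an assumed window. The entry is the median number registered between the 4th event and month 12.

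| Window (months) | Planned, p = 30 / 50 / 70% | 1 per month, p = 30 / 50 / 70% |
|---|---|---|
| 0.25-2 | 8 / 9 / 11 | 3 / 5 / 6 |
| 0.25-4 | 6 / 8 / 10 | 2 / 3 / 5 |
| 1-5 | 4 / 6 / 8 | 1 / 3 / 4 |

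The shorter windows suit injection-site pain, which qualifies after more than 1 week. The CRPS-pain route needs more than 1 month from treatment stop, so the longest window fits it better. A window of 0.25-1.25 months gives 9 / 10 / 12 at planned accrual. It could describe little but injection-site pain, so it is left out of the quoted range. Reporting time of up to seven days is not modelled.

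**The case against.** A reader might infer that a breach would go unseen for months. The documents do not support that. The trial is open label, AE forms arrive within seven days, and both events are asked about at each contact. The TMG monitors all aspects of conduct and meets about quarterly after set-up (Protocol 4.6). Under Protocol 10.10, suspicion of an unacceptable risk leads to suspension, with no wait for month 12. The IDSMC fixes its own schedule before recruitment starts and may meet sooner than annually. That schedule is not in the documents, so a 12-month gap is the permitted worst case and not a known plan. What stands against this is narrow: none of these routes is tied to the count in item 2, and none obliges anyone to compare it with the limit before month 12.

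A reader might also take 8 further starts as a floor. It is not. It needs planned accrual and a breach by about month 8; slower accrual or the slower CRPS-pain route gives fewer.

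Nor do the documents show that a breach is likely. They state no event rate, and at a true rate of 10% or 20% a breach is uncommon.

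Finally, the rules are advisory. Passing 3 of 10 calls for IDSMC judgement and a recommendation to the TSC, and later data on severity, resolution or later participants may inform it. That is correct, and it is a reason to let the IDSMC exercise that judgement promptly. It does not require the judgement to wait for a calendar date.

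**Conclusion.** The point holds in limited form. The month-12-or-later date is explicit in both documents, the criterion is settled at the 4th qualifying participant, and no document requires an IDSMC check of this count sooner. This is an improvable design choice and not a contradiction. The primary outcome and its analysis are unaffected.

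The size depends on accrual and event timing. Between the 10th registration and month 12, 8 more participants start at planned accrual and 2 at one per month. Given a breach at planned accrual, the median is about 4 to 11 further starts. That range rests on assumed event rates of 30-70% and on the three assumed timing windows; the figure of 8 rests on reading the second 12 months as months 7-18.

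**What to change.** Keep the limit, the month-12 assessment and the advisory status of the rules. Add to Protocol section 11 item 2, SAP 18.1.2 and SAP 25.1.2.2:

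*The trials unit keeps a running count; when a 4th of the first 10 registered participants has a qualifying event, the IDSMC is notified and reviews without waiting for month 12.*

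This brings the existing decision forward without altering which trials meet the criterion. It uses AE forms already received. The cost is a sentence in each place, a simple tally, and at most one unscheduled IDSMC review, held only if the limit has been passed. No automatic stop and no clinical rule is proposed. At the same amendment, Protocol 14.2.1 should say which months the second 12 months covers.
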